5.3 Lifestyle Considerations

5.3.1 Meals and Dietary Restrictions

Subjects should avoid eating a large meal for at least 2 hours prior to all lung function assessments at the centre.

Subjects should not eat or drink one hour prior to having the **CCI** test.

5.3.2 Activity

Subjects should avoid engaging in strenuous exertion for at least 30 minutes prior to all lung function assessments at the centre.

5.4 Screen Failures

Screen failures are defined as subjects who signed the ICF to participate in the clinical study but are not subsequently assigned to study treatment. A minimal set of screen failure information is required to ensure transparent reporting of screen failure subjects to meet the Consolidated Standards of Reporting Trials (CONSORT) publishing requirements and to respond to queries from regulatory authorities. Minimal information includes demography, screen failure details, eligibility criteria and any SAE.

Individuals who do not meet the criteria for participation in this study (screen failure) may be rescreened. Rescreen attempts are allowed in the study only if only if the reason for screen failure was transient (including but not limited to equipment failure, exclusion criterion #8 [Section 5.2], or other transient conditions) and the Study Physician has deemed that the reason for the rescreen is valid and has approved the rescreen.

Rescreened subjects should be assigned the same subject number as for the initial screening and be re-consented.

Rescreening should be discussed with the CRO Medical Monitor. If rescreening is performed within 30 days of initial screening, assessments from initial screening may be used, however clinically significant findings must be reassessed, and the subject must meet all entry criteria noted in the protocol. Subjects rescreened more than 30 days after initial screening must repeat all assessments and meet all entry criteria noted in the protocol.

6 STUDY INTERVENTION

Study intervention is defined as any investigational intervention(s), marketed product(s), placebo, or medical device(s) intended to be administered to a study subject according to the Clinical Study Protocol (CSP). Study intervention in this study refers to tezepelumab.

6.1 Study Intervention(s) Administered

6.1.1 Investigational Product

Investigational product details are provided in [Table 3](#).

Table 3 Investigational Product

Arm Name	Treatment 1
Intervention Name	Tezepelumab
Type	Drug
Dose Formulation	CCI [REDACTED]
Dosage Level	CCI [REDACTED]
Route of Administration	SC injection
Use	Experimental
IMP and NIMP	IMP
Sourcing	Provided centrally by the sponsor
Packaging and Labelling	Study intervention will be provided in single use 5 mL vials. Each vial will be labelled in accordance

Table 3 Investigational Product

	with GMP Annex 13 per country regulatory requirement.
Former Names	MEDI9929 and AMG 157

GMP Good Manufacturing Practice; IMP Investigational medical product; NIMP Non-investigational medical product; SC Subcutaneous.

6.2 Preparation/Handling/Storage/Accountability of Interventions

- 1 The Investigator or designee must confirm appropriate temperature conditions of 2°C to 8°C have been maintained during transit for all study intervention received and any discrepancies are reported and resolved before use of the study intervention.
- 2 Only subjects enrolled in the study may receive study intervention and only authorised site staff may administer study intervention. All study intervention must be stored in a secure, environmentally controlled, and monitored (manual or automated) area in accordance with the labelled storage conditions with access limited to the Investigator and authorised site staff.
- 3 The Investigator, institution, or the head of the medical institution (where applicable) is responsible for study intervention accountability, reconciliation and record maintenance (ie, receipt, reconciliation and final disposition records).

The IP will be supplied to the site in cartons with one vial of tezepelumab in each carton. Each vial as well as each carton will be labelled.

The IP kit will be allocated to the subject on a random basis by the site based on the available unused kits in the pharmacy.

The Investigator(s) will:

- 1 Obtain signed assent from the potential subject and consent from their guardian/legal representative, before any study specific procedures are performed.
- 2 Determine subject eligibility.
- 3 Assign the potential subject a unique enrolment number, ie, 'subject identification (SID) number'.

All unused supplies of IP will be destroyed by the site in accordance with their local Standard Operating Procedure (SOP). Investigational product destruction is not to be performed until approval has been granted by the sponsor.

Upon request by the site or following database lock (DBL), IQVIA will ask the sponsor for approval for the sites to destroy their IP. Approval from the sponsor will be forwarded to the

sites by the IQVIA site monitor.

6.2.1 Dose Preparation

Each vial should be visually inspected prior to dose preparation. The IP will be provided to the study sites as a colourless to slightly yellow clear solution contained in a 5 mL single use glass vial to be stored at 2°C to 8°C until used. If defects are noted with the IP, the Investigator and site monitor should be notified immediately. Preparation of IP must be performed by a qualified person (eg, pharmacist, Investigator or qualified designee) at the site.

Preparation of the IP is to be performed aseptically. Total in-use storage time from needle puncture of the IP vial to start of administration should not exceed 4 hours at room temperature. If storage time exceeds this limit, a new dose must be prepared from a new vial.

Dose preparation steps:

1. Allow the vial to equilibrate at room temperature (about 30 minutes to one hour).
Ensure that the vial is adequately protected from light during the warming process.
Gently swirl the vial to ensure the contents are mixed to a clear, homogeneous solution. Do not shake.
2. To prepare IP for administration remove the tab portion of the vial cap and clean the stopper with 70% ethyl alcohol or equivalent.
3. Attach a 21G 1½-inch sterile disposable needle to a 1 mL sterile syringe.
4. **CCI** [REDACTED]
5. Remove and discard the 21G 1½-inch sterile disposable needle from the syringe.
6. Attach a new 27G ½-inch sterile disposable needle to the same syringe in step 5.
7. Apply the appropriate label to the syringe according to local standard practice.

The assigned vial should be used only once to prepare a single dose required at the dosing visit. The IP does not contain preservatives and any unused product in opened and dispensed vials should not be used for subsequent dosing and should be stored until IP accountability has been completed as per the site's SOP. If the opened and dispensed vials must be discarded immediately after dose preparation as per the site's SOP, the vial labels along with the cartons must be retained for IP accountability.

The IP will be administered by one SC injection (see [Table 4](#)) according to standard practice. Standard numbing medications/devices and/or distraction techniques may be used with administration of IP.

Table 4 **Investigational Product Dose Preparation**

Dose	Number of vial(s) required	Syringe size required	Total volume administered
CCI	1	1 mL	CCI

The volume of IP drawn up and injected as well as any dosing issues encountered will be recorded in the electronic case report form (eCRF).

6.2.2 Dose Administration

If any of the following has occurred, the IP should not be administered:

- The subject received allergen immunotherapy injection within 7 days of scheduled IP administration.
- The subject has an intercurrent illness that in the opinion of the Investigator may compromise the safety of the subject in the study (eg, viral illnesses).
- The subject is febrile ($\geq 38^{\circ}\text{C}$; $\geq 100.4^{\circ}\text{F}$) within 72 hours prior to IP administration.

The visit should be rescheduled to another date and IP should be administered at that visit. Delay of the dosing visit can be extended for an additional 14 days.

The IP will be administered in the anterior thigh by a qualified healthcare professional (eg, Investigator or qualified designee) at the site. The injection site must be recorded in the source documents and in the eCRF. The person administering the dose will wipe the skin surface of the anterior thigh with alcohol and allow to air dry. The skin will be pinched to isolate the SC tissue from the muscle. The needle will be inserted at a 90-degree angle approximately halfway into the SC tissue. The IP will be slowly injected (no longer than 5 seconds duration is recommended) into the SC tissue using gentle pressure. The area should not be massaged after injection.

Note: Time of dispensing of IP, time IP taken out of the fridge and time of IP administration should be recorded in a specific log. This log must be a part of the subject's source documents.

Subjects should be observed for a minimum of 2 hours after administration of the IP for the appearance of any acute drug reactions (see [Appendix G](#)).

If the subject/parent/legal representative reports an injection site reaction, the Investigator or qualified designee will complete the AE eCRF page.

6.2.3 Procedures for Handling Incorrectly Enrolled Subjects

Subjects who fail to meet the eligibility criteria should not, under any circumstances, receive study IP. There can be no exceptions to this rule.

If a subject does not meet all the eligibility criteria but is enrolled in error, or incorrectly receives IP, the Investigator should inform the AstraZeneca Study Physician immediately. All subjects who receive study IP should remain in the study and the subjects should continue to be followed up in accordance with defined study procedures.

6.3 Measures to Minimise Bias: Randomisation and Blinding (Not applicable)

Blinding is not applicable as this is an open label, non-randomised study.

6.4 Study Intervention Compliance

When subjects are dosed at the site, they will receive study intervention directly from the Investigator or designee, under medical supervision. The date, and time if applicable, of dose administered in the clinic will be recorded in the source documents and recorded in the eCRF. The dose of study intervention and study subject identification will be confirmed at the time of dosing by a member of the study-site staff other than the person administering the study intervention.

The IP Storage Manager is responsible for managing the IP from receipt by the study site until the destruction of all unused IP. The date and time of all IP administrations should be recorded in the appropriate section of the eCRF.

6.5 Concomitant Therapy

Throughout the study, Investigators may prescribe concomitant medications or treatments (including rescue medication as required) deemed necessary to provide adequate supportive care. All use of concomitant medications and supplements (nutritional and prophylactic) will be recorded on the concomitant medication eCRF.

Any medication or vaccine (including over-the-counter or prescription medicines, vitamins and/or herbal supplements) that the subject is receiving at the time of enrolment or receives during the study must be recorded along with:

- Reason for use
- Dates of administration including start and end dates
- Dosage information including dose and frequency.

Refer to Section 8.1.1.1 for details of maintenance therapy restrictions on the days when lung

function testing is performed and to Section 8.1.2 for restrictions prior to the **CCI** test.

Asthma worsenings/exacerbations should be treated with oral, inhaled, or other medications (including corticosteroids and rescue medication) according to standard practice. The decision and the administration may be at the discretion of the Investigator and/or parent/legal guardian/subject upon temporary worsening of asthma signs and symptoms. In cases of asthma worsening/exacerbation, subjects should be evaluated at the study centre when feasible.

All medications taken for asthma or other conditions in the 6 months prior to Visit 1 must be recorded in the eCRF along with reason for treatment by the Investigator/authorised delegate at each visit.

The CRO Medical Monitor should be contacted if there are any questions regarding concomitant or prior therapy.

6.5.1 Restricted Medications

Restricted medications are shown in [Table 5](#).

Table 5 **Restricted Medications**

Restricted medication/class of drug	Usage
Asthma maintenance treatments	
Changes in either dose or regimen are discouraged from Visit 1 and throughout the study, unless there is an absolute medical need as judged by the Investigator.
 
Once daily LABA and LAMA should be withheld for at least 24 hours prior scheduled spirometry and CCI at site visits apart from any unscheduled visits due to asthma worsening.
 
Twice daily LABA- and LAMA-containing therapies should be withheld for at least 12 hours prior to scheduled spirometry and CCI at site.
 
LTRA should be restricted for at least 24 hours prior to scheduled spirometry and CCI at site.

Short-acting β 2-agonists (SABA)	
Regular scheduled use is not allowed from Visit 1 and preferably throughout the study, unless there is an absolute medical need as judged by the Investigator. As required (PRN) use is allowed; however, attention should be paid to the following restriction:
 
• If possible, SABA should be withheld at least 6 hours prior to scheduled spirometry, CCI and ECG. 
May be used for managing an asthma exacerbation event.

Short-acting antimuscarinics (SAMA; ipratropium)	If possible, SAMA should be withheld at least 6 hours prior to scheduled spirometry, CCI and ECG.
Inactive/killed vaccinations (eg, inactive influenza)	Allowed, provided they are not administered within 7 days before or after IP administration/Visit 2.

Table 5 Restricted Medications

Restricted medication/class of drug	Usage
COVID-19 vaccination	Allowed, provided that vaccination is not administered within 28 days before and 14 days after IP administration/Visit 2
Allergen immunotherapy	Allowed, if on stable therapy for at least 1 month prior to Visit 1 with no anticipated change during the study. This should not be administered within 7 days before or after IP administration/Visit 2.

ECG Electrocardiogram; CCI [REDACTED]; IP Investigational product; LABA Long-acting β 2-agonist; LAMA Long-acting muscarinic antagonist; LTRA Leukotriene receptor antagonist.

6.5.2 Prohibited Medications

Therapies excluded at screening and throughout the study (Section 5.2) are prohibited and may only be administered if necessary, to provide adequate supportive care (Table 6).

Table 6 Prohibited Medications

Prohibited medication/class of drug	Usage
Live Attenuated Vaccines	Not allowed 30 days prior to Visit 1 and preferably throughout the study. If there is an absolute medical need as judged by the Investigator, do not administer prior to 4 weeks after dose of IP.
Any systemic immunomodulators or immunosuppressives	Not allowed throughout the study, unless there is an absolute medical need as judged by the Investigator. Systemic corticosteroids may be used for managing an asthma worsening/exacerbation event.
Immunoglobulin or blood products	Not allowed 30 days prior to Visit 1 and throughout the study, unless there is an absolute medical need as judged by the Investigator.
Any marketed (eg, omalizumab, mepolizumab, reslizumab) or to be marketed, or investigational biologic treatment	Not allowed 4 months or 5 half-lives (whichever is longer) prior to Visit 1 and throughout the study.
Other investigational products (including investigational use of an approved drug)	Not allowed 30 days or 5 half-lives (whichever is longer) prior to Visit 1 and throughout the study, unless there is an absolute medical need as judged by the Investigator.
Medications not currently licensed for use in the treatment of asthma in children, (eg, theophylline), and not part of current standard of care	Not allowed from Visit 1 and throughout the study, unless there is an absolute medical need as judged by the Investigator.

IP Investigational product.

6.6 Dose Modification (Not applicable)

6.7 Intervention after the End of the Study

Subjects who complete Day 85/EOS should be given standard of care therapy at the discretion of the Investigator.

7 DISCONTINUATION OF STUDY INTERVENTION AND PARTICIPANT DISCONTINUATION/WITHDRAWAL

7.1 Discontinuation of Study Intervention

This is a single-dose study, therefore discontinuation from IP treatment is not applicable.

7.2 Participant Withdrawal from the Study

- A subject may withdraw from the study at any time at his/her or parent/legal representative's request or may be withdrawn at any time at the discretion of the Investigator for safety, behavioural, compliance, or administrative reasons. This is expected to be uncommon.
- A subject who considers withdrawing from the study should be encouraged to remain in the study and attend all study visits to have a minimum of AEs, SAEs and concomitant medication information collected. If the subject or parent/guardian does not agree to continue in-person study visits, modified follow-up options (eg, telephone contact with the subject or parent/guardian) should be arranged to ensure the collection of safety information through the Day 85 time point.
- At the time of withdrawal from the study, if possible, an EOS visit should be conducted, as shown in the SoA ([Table 1](#)). See SoA for data to be collected at the time of study withdrawal and follow-up and for any further evaluations that need to be completed.
- If the subject withdraws consent for disclosure of future information, the sponsor may retain and continue to use any data collected before such a withdrawal of consent.
- If a subject withdraws from the study, it should be confirmed if he/she or their parent/legal representative still agrees for existing samples to be used in line with the original consent. If he/she requests withdrawal of consent for use of samples, destruction of any samples taken and not tested should be carried in line with what was stated in the informed consent and local regulation. The Investigator must document the decision on use of existing samples in the site study records and inform the Global Study Team.

7.2.1 Replacement of Subjects

Subjects who are eligible to participate but do not go on to receive tezepelumab, or subjects who do not complete the required evaluations through to Day 85 may be replaced to maintain the stipulated number of evaluable subjects, at the discretion of the Sponsor.

7.3 Lost to Follow-up

A subject will be considered lost to follow-up if he or she repeatedly fails to return for

scheduled visits and is unable to be contacted by the study site.

The following actions must be taken if a subject fails to return to the clinic for a required study visit:

- The site must attempt to contact the subject and reschedule the missed visit as soon as possible and counsel the subject/parent/legal representative on the importance of maintaining the assigned visit schedule and ascertain whether or not the subject wishes to and/or should continue in the study.
- Before a subject is deemed lost to follow-up, the Investigator or designee must make every effort to regain contact with the subject/parent/legal representative (where possible, 3 telephone calls and, if necessary, a certified letter to the subject/parent/legal representative's last known mailing address or local equivalent methods). These contact attempts should be documented in the subject's medical record.

Discontinuation of specific sites or of the study are handled as part of [Appendix A](#).

8 STUDY ASSESSMENTS AND PROCEDURES

- Study procedures and their timing are summarised in the SoA ([Table 1](#)). Protocol waivers or exemptions are not allowed.
- Immediate safety concerns should be discussed with the IQVIA Global Therapeutic Medical Adviser immediately upon occurrence or awareness to determine if the subject should continue or discontinue in the study.
- Adherence to the study design requirements, including those specified in the SoA, is essential and required for study conduct.
- All screening evaluations must be completed and reviewed to confirm that potential subjects meet all eligibility criteria. The Investigator will maintain a screening log to record details of all subjects screened and to confirm eligibility or record reasons for screening failure, as applicable.

Planned sampled blood volume will be compliant with recommendations relating to GCP in the conduct of clinical trials ([European Commission 2008, Howie 2011](#)); the maximum amount of blood collected, including any losses in the manoeuvre, from each subject should not exceed 3% of the total blood volume during a period of 4 weeks and should not exceed 1% at any single time during the study ([Table 7](#)). Repeat or unscheduled samples may be taken for safety reasons or for technical issues with the samples.

Table 7 Maximum Volume of Blood to be Drawn from a Subject

Subject weight (kg)	Total blood volume (mL) ^a	Maximum blood volume (mL) to be drawn at any visit	Maximum blood volume (mL) to be drawn within a 4-week period
15-20	1200-1600	12.0-16.0	36.0-48.0
21-25	1680-2000	16.8-20.0	50.4-60.0
26-30	2080-2400	20.8-24.0	62.4-72.0
31-35	2480-2800	24.8-28.0	74.4-84.0
36-40	2880-3200	28.8-32.0	86.4-96.0
41-45	3280-3600	32.8-36.0	98.4-108.0
46-50	3680-4000	36.8-40.0	110.8-120.0
51-55	4080-4400	40.8-44.0	122.4-132.0
56-60	4480-4800	44.8-48.0	134.4-144.0
61-65	4880-5200	48.8-52.0	146.4-156.0
66-70	5280-5600	52.8-56.0	158.4-168.0
71-75	5680-6000	56.8-60.0	170.4-180.0
76-80	6080-6400	60.8-64.0	182.4-192.0
81-85	6480-6800	64.8-68.0	194.4-204.0
86-90	6880-7200	68.8-72.0	206.4-216.0
91-95	7280-7600	72.8-76.0	218.4-228.0
96-100	7680-8000	76.8-80.0	230.4-240.0

^a The total blood volume is estimated at 80 mL/kg body weight.

The total volume of blood to be drawn from each subject at each study visit is shown in [Table 8](#).

Table 8 Volume of Blood to be Drawn from Each Subject

Visit (Study day)	Sample	Sample blood volume (mL)	Visit total blood volume (mL)
Screening	Chemistry (including β -HCG if required)	3.5	10.5
	Haematology	2.0	
	Serology (HIV)	2.5	
	Hepatitis B/Hepatitis C	2.5	
V2 (Day 1)	Chemistry	3.5	15.5
	Haematology	2.0	
	PK	2.5	
	ADA	5.0	
	IgE	2.5	
V3 (Day 3)	PK	2.5	2.5
V4 (Day 7)	PK	2.5	2.5
V5 (Day 11)	PK	2.5	2.5
V6 (Day 15)	Chemistry	3.5	8.0
	Haematology	2.0	
	PK	2.5	
V7 (Day 29)	Chemistry	3.5	15.5
	Haematology	2.0	
	PK	2.5	
	ADA	5.0	
	IgE	2.5	
V8 (Day 57)	PK	2.5	2.5
V9 (Day 85/EOS)	Chemistry	3.5	15.5
	Haematology	2.0	
	PK	2.5	
	ADA	5.0	
	IgE	2.5	
Total blood volume (mL)			75.0

Volumes exclude serum pregnancy testing (with the exception of Visit 1) and exclude any re-testing requirements. If serum pregnancy testing is needed at any other visits, then an additional 2.5 mL blood collection will be required.

[figure not shown]
ADA Anti-drug antibodies; β -HCG Beta-human chorionic gonadotrophin; EOS End of Study; HIV Human immunodeficiency virus; IgE Immunoglobulin E; PK Pharmacokinetic; V Visit.

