5.1 Inclusion Criteria

Subjects are eligible to be included in the study only if all of the following criteria apply:

Informed Consent

- 1 Written informed consent and written informed assent and any locally required authorisation obtained from the subject and legal representative prior to any study-related procedure taking place.

The informed consent form (ICF) process is described in Appendix [A 3](#).

Age

- 2 Age 5 to 11 years (inclusive) at Visit 1 and Visit 2 (Day 1).

Type of Subject and Disease Characteristics

- 3 Documented physician diagnosed asthma, defined by the regional guidelines (ie, National Institutes of Health [NIH], GINA, American Thoracic Society [ATS], European Respiratory Society [ERS], etc), for at least 6 months prior to Visit 1. If the subject is naïve to the study site, the participant/guardian must self-report a physician diagnosis of asthma and the investigator must confirm by review of medical history with the participant/guardian.
- 4 Documented treatment with total daily dose of either low, medium, or -high-dose ICS ($\geq 100 \mu\text{g}$ fluticasone propionate dry powder inhaler [DPI] or equivalent; see [Appendix H](#)) for at least 6 months, as described in Step 2 to Step 4 of GINA guidelines ([GINA 2020](#)) with stable dose for at least 3 months prior to Visit 1.
- 5 Additional controller medication according to standard practice of care is permitted (LABA, leukotriene receptor antagonist [LTRA], long-acting muscarinic antagonist [LAMA] only) and must be documented and stable for at least 3 months prior to Visit 1.
- 6 Inclusion criterion 6 (historical or current airway reversibility) removed with version 3.0 of Clinical Study Protocol.
- 7 Pre-bronchodilator (BD) FEV₁ of $\geq 50\%$ of predicted normal value at Visit 1.
- 8 If on allergen immunotherapy, subjects must be on stable maintenance dose and schedule ≥ 1 month prior to Visit 1.
- 9 Able and willing to comply with the requirements of the protocol.
- 10 Acceptable inhaler and spirometry techniques during screening/run-in period as assessed by the Investigator.

Weight

- 11 Body weight \geq 16 kg at Visit 1 and Visit 2 (Day 1).
- 12 Inclusion criterion 12 (Body mass index for age and percentiles) removed with version 4.0 of Clinical Study Protocol.

Sex

- 13 Male or female.

Reproduction

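### Table 8's fixed 15.5 mL draws at V2, V7 and V9 exceed the protocol's own 1% blood limit for any child under 19.375 kg, and criterion 11 admits children from 16 kg

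*Protocol*

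**What the plan says.** Protocol Section 8 makes a compliance statement: "Planned sampled blood volume will be compliant with recommendations relating to GCP in the conduct of clinical trials". The limit then set is that each child's sampled volume "should not exceed 3% of the total blood volume during a period of 4 weeks and should not exceed 1% at any single time", and blood lost during sampling counts toward it. Footnote a to Table 7 supplies the conversion: "The total blood volume is estimated at 80 mL/kg body weight". Table 7 turns the 1% figure into a maximum per visit and the 3% figure into a maximum per 4 weeks, in weight bands. The lowest band, 15-20 kg, shows 12.0-16.0 mL per visit and 36.0-48.0 mL per 4 weeks.

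Table 8 is introduced with "The total volume of blood to be drawn from each subject at each study visit is shown in" and has a single set of volumes for all weights. V2, V7 and V9 each total 15.5 mL. Its footnote adds: "Volumes exclude serum pregnancy testing (with the exception of Visit 1) and exclude any re-testing requirements".

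Section 5.1, criterion 11, sets a minimum weight of 16 kg at Visits 1 and 2. Section 9.2 asks for at least 4 subjects under 25 kg.

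**The concern.** The limit scales with weight and the schedule does not. At the lightest admissible weights the planned draw is larger than the maximum the same section promises. Table 7 hides this, because a band of 12.0-16.0 mL looks as if it allows 15.5 mL for any child of 15-20 kg, when the upper figure applies only at 20 kg.

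The limit is a protection for children aged 5 to 11 who receive one dose in a study where Section 2.3.2 says therapeutic benefit cannot be predicted. A site with a 17 kg child cannot follow both Table 8 and the limit. It could draw smaller tubes, omit a sample or go over. The visible text does not say which sample gives way, so sites may act differently.

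**Working it through.** **Inputs.** Limits of 1% and 3%, and 80 mL/kg (Section 8 and Table 7 footnote); visit volumes (Table 8); minimum weight 16 kg (criterion 11); screening Day -14 to -1, V4-V6 ±1 day, V7 ±2 days (Schedule of Activities).

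**Reproducing the plan's figures.** V2, V7 and V9: 3.5 + 2.0 + 2.5 + 5.0 + 2.5 = 15.5 mL. Study total: 10.5 + 15.5 + 3 × 2.5 + 8.0 + 15.5 + 2.5 + 15.5 = 75.0 mL, as printed. Table 7, lowest band: 15 × 80 × 1% = 12.0 and 20 × 80 × 1% = 16.0 mL; at 3%, 36.0 and 48.0 mL. These also agree.

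**Per-visit limit.** Limit = 0.8 × weight. Break-even weight = 15.5 / 0.8 = 19.375 kg.

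| Weight (kg) | Limit (mL) | 15.5 mL as % of blood volume | Excess (mL) |
|---|---|---|---|
| 16 | 12.8 | 1.21 | 2.7 |
| 17 | 13.6 | 1.14 | 1.9 |
| 18 | 14.4 | 1.08 | 1.1 |
| 19 | 15.2 | 1.02 | 0.3 |
| 19.375 | 15.5 | 1.00 | 0 |
| 20 | 16.0 | 0.97 | none |

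Every other visit takes 10.5 mL or less, which complies from 10.5 / 0.8 = 13.125 kg. The result does not depend on timing. Losses and re-tests would raise the break-even weight.

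**Four-week limit.** Limit = 2.4 × weight, so 38.4 mL at 16 kg.

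- V1-V5: 10.5 + 15.5 + 7.5 = 33.5 mL. Break-even 33.5 / 2.4 = 13.96 kg, so no breach.
- V1-V6: 33.5 + 8.0 = 41.5 mL. Breach below 41.5 / 2.4 = 17.3 kg.
- V2-V7: 15.5 + 7.5 + 8.0 + 15.5 = 46.5 mL. Breach below 46.5 / 2.4 = 19.375 kg.

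Which total applies depends on the days. There is no Day 0, so Day -k to Day d spans k + d calendar days. On a 28-calendar-day count with V6 on Day 15, V1-V6 fall together when screening is on Days -13 to -1. V2-V7 fall together when V7 is on Day 27 or 28. If Day 1 and Day 29 are both allowed inside the 4 weeks, the 46.5 mL total applies on target days as well.

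**Permitted timings.** There are 14 screening days × 3 × 3 × 3 (V4, V5, V6) × 5 (V7) = 1,890 day combinations. On the 28-calendar-day count the largest 4-week total is 33.5 mL in 81, 41.5 mL in 1,053, 46.5 mL in 729 and 57.0 mL in 27. At 16 kg the limit is therefore exceeded in 1,053 + 729 + 27 = 1,809 (96%). At 18-19 kg it is exceeded in 729 + 27 = 756 (40%). Allowing 28 elapsed days, the shares are 99% and 60%. These are counts of combinations, not probabilities. They assume one screening draw and no dosing delay.

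**The case against.** The protective rule is in the protocol, and Table 7 gives sites a maximum by weight. Section 8 allows no waivers. The Schedule of Activities lists samples, not millilitres, so a site that draws smaller tubes meets both the schedule and Table 7; only Table 8's planned volume is missed. The number of such children may be zero, because children of 20-24 kg can fill the quota under 25 kg. The Laboratory Manual, the redacted schedule footnotes and an unreproduced figure beside Table 8 may also carry site instructions.

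Much of this stands, and it lowers the severity. It does not remove the contradiction. Section 8 says that planned volumes comply, and for an eligible child of 16 kg to under 19.375 kg they do not. Splitting a draw within a visit does not help, because Table 7 caps the visit total. An instruction elsewhere would still leave Table 8 inconsistent with Section 8.

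A reader might infer that children will be overdrawn, that PK data will be lost, or that the 3% limit fails in every case. The documents support none of these. Enrolled weights are not known, the caps may be respected in practice, and PK is only 2.5 mL of each 15.5 mL draw. On target days, screening on Day -14 gives 33.5 mL and no 4-week breach on the 28-calendar-day count. A dosing delay ("Delay of the dosing visit can be extended for an additional 14 days") can also move screening out of the period. The 57.0 mL total for V1-V7, which would reach children up to 57.0 / 2.4 = 23.75 kg, is remote. On that count it needs screening on Day -1 and V7 on Day 27, with central-laboratory virology back within a day.

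**Conclusion.** Wrong as written; should be fixed. Table 8's 15.5 mL at V2, V7 and V9 exceeds the protocol's 1% limit for any child under 19.375 kg at that visit. At the 16 kg minimum the excess is 2.7 mL (1.21% of blood volume) before losses and re-tests. The calculation uses weight at the visit, which is an assumption because Section 8 does not say which weight governs. The 16 kg floor applies only at V1 and V2, so the excess at V7 or V9 could be smaller or larger than 2.7 mL.

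The 3% limit is a secondary finding. It depends on timing and on an undefined count of 4 weeks, but for the lightest children most permitted timings breach it.

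The severity rests on the child-protection limit alone. No clinical harm and no effect on the primary PK analysis is shown, and the affected group may be empty.

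**What to change.** 1. Add a reduced-volume column to Table 8 for children under about 20 kg at the visit. It should keep each visit total below 0.8 mL/kg (at most 12.8 mL at 16 kg) with a margin for losses. Use smaller tube volumes confirmed by the laboratory, or omit the lowest-priority non-PK sample chosen by the sponsor. Dropping the 2.5 mL IgE sample alone is not enough at 16 kg: 15.5 - 2.5 = 13.0 mL, which complies only from 13.0 / 0.8 = 16.25 kg. The documents do not rank IgE against ADA, since the exploratory endpoints are redacted.
2. State that a per-visit cap of 0.8 mL/kg and a rolling 4-week cap of 2.4 mL/kg, on actual weight, take precedence over Table 8. Count losses, re-tests and any rescreening draw. Section 5.4 allows rescreening, and a second 10.5 mL draw within the same 4 weeks would take V1-V6 from 41.5 to 52.0 mL. Say how 4 weeks is counted, and give the order in which samples are withheld, with PK kept.

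While Table 7 is open, correct one cell: 46 kg × 2.4 = 110.4 mL, where 110.8 is printed. This does not affect the point.

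The cost is a small amendment to Section 8 and its tables and a Laboratory Manual update, with no extra subjects or procedures. Weight is already measured at V2, V7 and V9. The downside is that a non-primary sample such as IgE may be lost, or tube volumes reduced, in the lightest children.
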